9.6 OFF TREATMENT AND OFF STUDY CRITERIA

All subjects will go off study after 5-year NIH landmark visit.

Subject choice: Subjects may be removed from study at their request at any time. The risks of withdrawing will be discussed, as will alternative treatment options. The risks of withdrawing from the study including high mortality rate with supportive care only (if that is chosen) will be discussed in detail with the patient. Those subjects who choose to

Abbreviated Title: Early Initiation of Oral Therapy for Naïve Severe Aplastic Anemia (SAA)

Version Date: 11/05/2025

withdraw will be strongly encouraged to continue to have blood counts monitored until initiation of alternative SAA therapy or through the 6 months off study medication to assess for late occurring adverse events.

Principal investigator decision: Should any of the following events occur, study drug administration will be discontinued, and the subject will be followed until resolution of the event and labs will be monitored at least every week or as clinically indicated until he/she initiates alternative SAA therapy or through 6 months off study drug time point. Appropriate clinical experts such as ophthalmologist, etc. will be consulted as deemed necessary.

Adverse events related to:

- Death or any grade IV adverse event considered to be probably or definitely related to EPAG
- Life threatening acute hypersensitivity reactions
- Intolerance of eltrombopag not resolved by dose reduction
- Thrombosis/embolism (DVT, PE, stroke or TIA, myocardial infarction) other than line associated thrombosis
- Persistent hepatotoxicity as defined in section 6.4.2
- Infusion-related h-ATG reactions refractory to all appropriate supportive measures

Should any of the following events occur, study drug administration will be discontinued, and the subject will be taken off study.

Clonal evolution or relapse:

- Evidence of a poor risk clonal disorder (chromosome 7 abnormalities or complex cytogenetics) at any time while on study
- Evidence of myelodysplastic syndrome or AML according to WHO criteria at any time while on study
- Relapse criteria are met and treatment other than CsA and EPAG are started

Other

- Persistent non-compliance or lost to follow-up per PI discretion*
- Patients who require chemotherapeutic treatment or require drugs with hematological effects
- Initiation of additional immunosuppressive therapy other than steroids or cyclosporine (if beyond 6 months then mycophenolate mofetil can also be administered per PI discretion in patients who cannot tolerate cyclosporine and who require immunosuppression) or if beyond 2 years, enroll in other available clinical trials.

Pregnancy: This protocol does not enroll patients who are pregnant or women of child-bearing potential unless they are using contraception during the study treatment period (Section 4.3).

Because aplastic anemia is a disease of young adults, if a woman becomes pregnant while participating in the study despite stringent contraception requirements and education by the study team regarding the risks of relapsed aplastic anemia with pregnancy upon study entry and at

Abbreviated Title: Early Initiation of Oral Therapy for Naïve Severe Aplastic Anemia (SAA)

Version Date: 11/05/2025

every landmark visit, patient may remain on study. This limited inclusion of pregnant women on this study permits capture of the secondary endpoint (relapse of aplastic anemia) without exposing the subject/fetus/neonate to study drugs or invasive protocol procedures.

- If a patient becomes pregnant while on study drugs (CSA and/or EPAG), patient will discontinue the medications immediately but may remain on study
- If a patient becomes pregnant during follow-up period and not on any study treatments, patient may remain on study
- No investigational interventions or research procedures will be performed during pregnancy (if landmark visit is due during pregnancy, it will be delayed till after). All clinical decisions about pregnancy management will be made by the patient and the treating physician.
- If a patient relapses with aplastic anemia during pregnancy, no treatment will be provided on study; recommendations will be provided to the local treating physician for clinical management and if pursued any treatment other than supportive care (transfusions), patient will be taken off study
- Blood count monitoring with complete blood counts (CBCs) will be obtained with increased frequency than otherwise indicated, especially in later gestation, to monitor for AA relapse
- Fetus/neonate is not a research subject in this protocol
- No inducements, monetary, or otherwise, will be offered to terminate a pregnancy
- Individuals engaged in the research will have no part in any decisions as to the timing, method, or procedures used to terminate a pregnancy.
- Individuals engaged in the research will have no part in determining the viability of a neonate.
- At the conclusion of pregnancy, participant may remain on study, and resume protocol procedures for both safety and efficacy endpoints.

*Please note that subjects not following up at the Clinical Center by 8 weeks or who fail to comply with the recommended oral treatment or clinical laboratory assessment may be taken off the study. However, per PI discretion, a “grace period” of additional 4 weeks may be granted if a patient is unable to present to the CC due to logistical reasons beyond their control such as inability to obtain visa, critical illness requiring hospitalizations etc., so long as they are responding to the oral treatment. During special circumstances such as COVID 19 outbreak, “grace period” may be extended up to 6 months per PI discretion.

Once off study, subjects will be referred back to the referring physician or consented to the NHLBI Standard of Care protocol (20H0099) for consideration for standard therapy or they may be evaluated for eligibility for another NIH protocol, depending on what is considered to be in the best interest of the subject.

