9.2 SECONDARY ENDPOINTS

Secondary endpoints will be: (a) hematological response at 1, 2, 3, 6 and 12 months and yearly thereafter; (b) relapse; (c) clonal evolution to PNH, clonal chromosomal population in bone marrow, myelodysplasia by morphology, or acute leukemia; (d) overall survival; (e) hematological response of relapse subjects that re-start treatment with cyclosporine and/or eltrombopag; (f) freedom from h-ATG.

Abbreviated Title: Early Initiation of Oral Therapy for Naïve Severe Aplastic Anemia (SAA)

Version Date: 11/05/2025

Subjects will be followed up to 60 months so that long-term disease-free and overall survival can be estimated. Response and toxicity comparisons will be made with previous IST combined with eltrombopag protocol (12-H-0150)

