9.4 STATISTICAL METHODS

The planned analyses will be based on the “intention-to-treat” principle and include descriptive statistics on the proportions of feasible patients. The feasibility probability will be estimated using the sample proportion, and its inferences, including confidence intervals and hypotheses testing, will be evaluated using Binomial distributions. Survival analysis for time-to-death and time-to-response will include methods based on the Kaplan-Meier estimates and the Cox Proportional Hazard regression. If it is appropriate, we will consider additional analyses for the primary and secondary endpoints using the analysis of variance, multiple regression and logistic regression models. Graphical tools will be used to display the appropriate estimates (i.e.

Abbreviated Title: Early Initiation of Oral Therapy for Naïve Severe Aplastic Anemia (SAA)

Version Date: 11/05/2025

estimated proportions and the Kaplan-Meier curves) and their corresponding 95% confidence intervals.

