10.6.2 Duration of Serious Adverse Event Collection

The collection of SAEs will begin on the first day of initiation of the study drug and will continue as long as the subject is on study. Starting 30 days after the 6 month landmark visit or 30 days after treatment is discontinued (if before the 6 month landmark visit), SAEs will only be captured in the research database when deemed possibly, probably or definitely related to the study treatment.

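### Section 9.6 takes patients off study at poor-risk clonal evolution or MDS/AML with no stated vital-status follow-up; if they are censored at exit, 60-month overall survival is biased upward

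*Combined protocol and SAP*

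**What the plan says.** OS is secondary endpoint (d) in 9.2, which gives the reason for long follow-up: "Subjects will be followed up to 60 months so that long-term disease-free and overall survival can be estimated". Section 9.4 states an intention-to-treat principle in general terms and names the tools: "Survival analysis for time-to-death and time-to-response will include methods based on the Kaplan-Meier estimates and the Cox Proportional Hazard regression". It does not say when a patient is censored for OS.

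Section 9.6 contains two different lists.

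- **Adverse events.** Drug stops, the event is followed to resolution, and laboratory monitoring continues until other therapy starts or until six months off drug.
- **Clonal evolution, relapse and other reasons.** The rule is stronger: "Should any of the following events occur, study drug administration will be discontinued, and the subject will be taken off study". The triggers include "Evidence of a poor risk clonal disorder (chromosome 7 abnormalities or complex cytogenetics) at any time while on study"; MDS or AML by WHO criteria; "Relapse criteria are met and treatment other than CsA and EPAG are started"; and "Initiation of additional immunosuppressive therapy other than steroids or cyclosporine", with an exception after six months for mycophenolate in cyclosporine-intolerant patients.

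After exit, 9.6 provides for referral back to the referring physician, consent to a standard-of-care protocol, or evaluation for another NIH protocol. It states no return of data to this study. Section 10.6.2 says that SAE collection "will continue as long as the subject is on study".

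Two groups are handled differently. Patients whose relapse is retreated with CsA and/or EPAG stay on study, with visits at least annually to five years (6.8). Patients who become pregnant stop drug but may remain on study, expressly so that relapse can still be captured (9.6).

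**The concern.** A 60-month OS estimate needs to know who is alive at 60 months. The off-study rule removes patients at the events that most plainly signal a worse prognosis, and the protocol does not say how a death after exit would reach the database. An intention-to-treat statement cannot recover data that were not collected.

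Kaplan-Meier and Cox methods assume that a censored patient has the same future risk of death as a comparable patient still under observation. Section 2.3.7 names high-risk clonal evolution as a leading source of mortality in patients treated with immunosuppression, so that assumption would fail for patients who leave because of it. The reported curve would then describe mainly patients who did not evolve, while being labelled as the survival of all enrolled patients.

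**Working it through.** **Is there a route for deaths after exit?** The sections that could supply one do not.

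- 9.2 sets the horizon but gives no procedure for patients who have left.
- 9.4 gives the principle and the methods, with no censoring rule.
- The adverse-event list in 9.6 provides follow-up, but of events and laboratory values, and only for that list.
- The post-exit paragraph of 9.6 describes where care goes, not what is reported back.
- 6.8 covers only patients retreated with CsA and/or EPAG.

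**Size.** The plan gives no OS target, expected rate or number of deaths, so there is no figure to reproduce. The following is an illustration only.

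Inputs:

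- *f*, share leaving: 8% to 15%. The 8% is the one-year high-risk evolution rate in 12-H-0150 (9.3). The 15% is the approximate clonal evolution rate quoted in 2.3.5. Neither is an exit rate. The 15% includes cytogenetic changes that do not force exit, and neither figure counts salvage exits.
- *s*, five-year survival while on study: 80% to 90%, borrowed from the figure for responders to immunosuppression in 2.3.2.
- *m*, five-year mortality after exit: 30% to 50%. **Assumed**; the documents give no figure.
- *W*, period over which exits are spread evenly: five years or two years. **Assumed**.

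With constant hazards a = -ln(s)/5 on study and b = -ln(1-m)/5 after exit:

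True OS(5) = (1-f)·s + f·G, where G = (1/W) × integral from 0 to W of exp(-a·t)·exp(-b·(5-t)) dt = exp(-5b)·[exp((b-a)W) - 1] / [(b-a)W].

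Kaplan-Meier censored at exit estimates s, so the overstatement is s - OS(5).

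Worked case: f = 0.15, m = 0.50, s = 0.90, W = 5.

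- a = 0.02107, b = 0.13863, (b-a)W = 0.5878.
- G = 0.5 × (1.800 - 1)/0.5878 = 0.6805.
- OS(5) = 0.85 × 0.90 + 0.15 × 0.6805 = 0.7650 + 0.1021 = 0.8671.
- Overstatement = 90.00 - 86.71 = 3.29 points.

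| f | m | s | Overstatement, W = 5 | Overstatement, W = 2 |
|---|---|---|---|---|
| 8% | 30% | 80% | 0.41 | 0.65 |
| 8% | 30% | 90% | 0.83 | 1.31 |
| 8% | 50% | 80% | 1.29 | 2.00 |
| 8% | 50% | 90% | 1.76 | 2.69 |
| 15% | 30% | 80% | 0.77 | 1.21 |
| 15% | 30% | 90% | 1.56 | 2.45 |
| 15% | 50% | 80% | 2.43 | 3.75 |
| 15% | 50% | 90% | 3.29 | 5.04 |

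In a study of 80, the extremes correspond to 0.0041 × 80 = 0.3 and 0.0504 × 80 = 4.0 patients.

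**Sensitivity to the assumption.** A second model used a constant exit rate, 90% on-study five-year survival and two-year post-exit survival anywhere from 30% to 90%. It gives 0.5-4.9 points at 8% leaving and 1.0-9.3 points at 15%. The assumed post-exit survival therefore largely drives the size.

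**Direction.** If b = a, then G = s and the overstatement is zero. If b < a, the sign reverses. The upward direction therefore needs a higher death rate after exit than before it.

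**The case against.** **Nothing says patients are censored at exit.** True. Section 9.2 speaks of subjects in general and 9.4 of intention-to-treat, so the team may intend to trace everyone. The bias is conditional on censoring at exit. But neither sentence provides a mechanism or overrides 9.6, so the gap stands.

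**The SAE window proves little.** This stands. Under 10.6.2, from 30 days after the six-month visit (or after earlier discontinuation of treatment), only SAEs at least possibly related to treatment enter the research database. An unrelated late death in a patient still on study would not arrive by that route either. SAE reporting is not shown to be the source of OS data, so its end at exit should not carry the argument. The argument rests on the absence of any stated vital-status collection.

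**Stronger readings to avoid.**

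- A reader might infer that 9.2 and 9.6 contradict each other. They do not: follow-up is up to 60 months, which allows earlier exit.
- A reader might infer that salvage and added-immunosuppression exits also push OS upward. No section gives higher mortality after those exits, and 2.3.1 describes favourable survival after transplantation in younger patients.
- A reader might take the Early group's 3.8% as the share who leave. It is a one-year high-risk evolution rate and does not count salvage exits.

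**The consequence is limited.** Largely so. OS is one of six secondary endpoints, with no target, power or decision rule, and 9.2 plans comparisons with 12-H-0150 for response and toxicity, not OS. At N = 80 and 90% survival the simple 95% half-width is 1.96 × √(0.9 × 0.1/80) = 6.6 points, wider than every value in the table. The bias would, however, add to that uncertainty rather than be covered by it.

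**Conclusion.** The point holds as a conditional one. Section 9.6 takes patients off study at poor-risk cytogenetics and MDS/AML (and at certain salvage or immunosuppressive treatments), and followed as written it leaves later deaths with no stated route into the OS data. If those patients are censored at exit, the censoring is informative for high-risk evolution and MDS/AML, on the protocol's own account of their prognosis, and Kaplan-Meier OS is biased upward. For the remaining exits the direction is open.

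The table's ranges rest on assumed post-exit mortality and exit timing and on proxies for the other two inputs. They show that the effect could run from negligible to several points; they do not estimate it.

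The primary feasibility test is unaffected. So is the high-risk evolution count, because the event is recorded before it causes the patient to leave. The change is worth making because OS is a stated endpoint and vital status not tracked now may be hard to recover later.

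**What to change.** Leave the treatment-stopping criteria as they are and change only data collection and analysis.

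- **Section 9.6:** separate off-treatment from off-study for data collection, as the pregnancy rule already does. For all enrolled patients, except those who withdraw consent for contact, collect vital status and the date of transplant or other salvage at least yearly to 60 months, by telephone or home-physician records.
- **Section 9.4:** state that OS is censored only at the date last known alive, and not at clonal evolution, salvage therapy or going off study. Add a sensitivity analysis for patients whose vital status after exit cannot be obtained.

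The cost is protocol wording and about one contact or record request per year for each patient who leaves: at the illustrative 8-15% of 80, that is 0.08 × 80 = 6.4 to 0.15 × 80 = 12 patients. A consent addition may be needed if continued contact is not already covered; the consent pages were not available to check.

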10 SAFETY AND OTHER ASSESSMENTS

10.1 SAFETY MONITORING

Principal Investigator: Accrual, efficacy and safety data will be monitored by the Principal Investigator, [name]. Quality assurance and control monitoring will be consistent with the NHLBI Division of Intramural Research Clinical Research Quality Assurance and Quality Control Policy.

NHLBI DSMB: The NHLBI Data Safety and Monitoring Board will review the protocol at 6 to 12 month intervals. A progress report will be forwarded to the DSMB at these times and their recommendations will be expeditiously implemented. The DSMB may recommend early termination of the study for considerations of safety and efficacy.

Novartis: An annual progress report, any amendment to the protocol, and any change in the status of the protocol will be forwarded to Novartis.

10.2 ASSESSMENT OF SAFETY

Definitions

Adverse Event (AE): Any untoward medical occurrence in a human subject, including any abnormal sign (e.g., abnormal physical exam or laboratory finding), symptom, or disease, temporally associated with the subject's participation in the research, whether or not considered related to the subject's participation in the research (21 CFR 312.32 (a)).

Non-hematologic abnormal laboratory findings used to evaluate the safety of this protocol regimen will include any change from laboratory assessments done prior to first dose of study medication that result in a progression to a grade 3 or 4 laboratory toxicity or are characterized by any of the following:

- Results in discontinuation from the study
- Is associated with clinical signs or symptoms
- Requires treatment or any other therapeutic intervention
- Is associated with death or another serious adverse event, including hospitalization
- Is judged by the Investigator to be of significant clinical impact
- If any abnormal laboratory result is considered clinically significant, the investigator will provide details about the action taken with respect to the test drug and about the patient's outcome.

Serious Adverse Event (SAE): An adverse event or suspected adverse reaction is considered "serious" if, in the view of either the investigator or sponsor, it results in any of the following outcomes:

- results in death;
- is life-threatening (places the subject at immediate risk of death from the event as it occurred);
- results in in-patient hospitalization or prolongation of existing hospitalization;
- results in a persistent or significant incapacity;
- results in a congenital anomaly/birth defect; or

Abbreviated Title: Early Initiation of Oral Therapy for Naïve Severe Aplastic Anemia (SAA)

Version Date: 11/05/2025

- based upon appropriate medical judgment, may jeopardize the subject's health and may require medical or surgical intervention to prevent one of the other outcomes listed in this definition.

Suspected adverse reaction: Suspected adverse reaction means any adverse event for which there is a reasonable possibility that the drug caused the adverse event. For the purposes of IND safety reporting, 'reasonable possibility' means there is evidence to suggest a causal relationship between the drug and the adverse event. A suspected adverse reaction implies a lesser degree of certainty about causality than adverse reaction, which means any adverse event caused by a drug.

Unexpected adverse reaction: An adverse event or suspected adverse reaction is considered "unexpected" if it is not listed in the investigator brochure or is not listed at the specificity or severity that has been observed; or, if an investigator brochure is not required or available, is not consistent with the risk information described in the general investigational plan or elsewhere in the current application. "Unexpected", also refers to adverse events or suspected adverse reactions that are mentioned in the investigator brochure as occurring with a class of drugs or as anticipated from the pharmacological properties of the drug but are not specifically mentioned as occurring with the particular drug under investigation.

Unanticipated problem (UP): Any incident, experience, or outcome that meets all of the following criteria:

- **Unexpected** in terms of nature, severity, or frequency in relation to
 - the research risks that are described in the IRB-approved research protocol and informed consent document; Investigator's Brochure or other study documents; and
 - the characteristics of the subject population being studied; and
- **Related or possibly related** to participation in the research; and
- Places subjects or others at a **greater risk of harm** (including physical, psychological, economic, or social harm) than was previously known or recognized.

Unanticipated Problem that is not an Adverse Event: An unanticipated problem that does not fit the definition of an adverse event, but which may, in the opinion of the investigator, involves risk to the subject, affect others in the research study, or significantly impact the integrity of research data. For example, report occurrences of breaches of confidentiality, accidental destruction of study records, or unaccounted-for study drug.

Protocol Deviation (PD): Any change, divergence, or departure from the IRB approved research protocol.

Non-compliance: The failure to comply with applicable NIH HRPP policies, IRB requirements, or regulatory requirements for the protection of human research. Noncompliance may be further characterized as:

1. Serious non-compliance: Non-compliance that:
 - a. Increases risks, or causes harm, to participants
 - b. Decreases potential benefits to participants
 - c. Compromises the integrity of the NIH HRPP
 - d. Invalidates the study data

Abbreviated Title: Early Initiation of Oral Therapy for Naïve Severe Aplastic Anemia (SAA)

Version Date: 11/05/2025

2. Continuing non-compliance: Non-compliance that is recurring. An example may be a pattern of non-compliance that suggests a likelihood that, absent an intervention, non-compliance will continue. Continuing noncompliance could also include a failure to respond to IRB requests to resolve previous allegations of non-compliance.
3. Minor (non-serious) non-compliance: Non-compliance that, is neither serious nor continuing. Safety assessments will consist of monitoring and recording AEs and SAEs; measurements of protocol-specified hematology, clinical chemistry, and other laboratory variables; measurement of protocol-specified vital signs; and other protocol-specified tests that are deemed critical to the safety evaluation of the study drug.

